## **Brief Purpose of Study**

This study is designed to examine whether In Vivo nicotine replacement therapy (NRT) experience intervention will be effective in quitting smoking as compared to behavioral standard of care smoking cessation treatment. For this study, In Vivo experience is: the use of one of four different short-acting NRT products in conjunction with nicotine patches during session. Specialized counseling focused around the experience of NRT, including how the use of NRT may help with quitting smoking, side effects, and smoking cessation expectancies will also be utilized.

If eligible to participate, subjects will be randomized into one of the four Intervention (In-Vivo) groups or the control group. They will be asked to fill out forms regarding smoking behavior, demographics, medical information, and a contact sheet. Some questionnaires will be repeated at every visit and others will be repeated less frequently. Participants are asked to complete 13 weeks of intervention, comprised of five weeks of smoking cessation therapy (Intervention or Control; Weeks 1-5) and three treatment sessions designed to measure medication adherence (Weeks 6, 9 and 13). Following intervention completion, participants will be asked to return for a follow up visit at one month.

Participants in the Intervention groups will be asked to go as long as they can without smoking the day of the therapy sessions. They will put a nicotine patch on during each of the weekly sessions. During the first four weekly sessions, participants in the Intervention groups will also use a different form of short-acting NRT each week (nicotine gum, lozenge, inhaler, nasal spray) and in the fifth week, will select which short-acting medication they would prefer to use for the duration of the study. Participants will discuss the experience of wearing the patch and/or using the short-acting NRT while they are in session. The Control group will not use NRT medication during the sessions but will be given standard counseling regarding quitting smoking.

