**sure to emphasize they are not to use the lozenges on the morning of the next appointment.**

21. Have the participant sign for the medication in the medication sign-out log.
22. Mark in the Medication Inventory binder how many of the patches and quit tubes you have given out so that we maintain a running total of prescriptions we have on hand.
23. Remind the participant of the instructions on how to use the patches and lozenges and let them know they can reference their workbook if they forget. Give the participant the instructions sheet.
24. Compensate the participant on their Greenphire ClinCard.
25. Give the participant an appointment card. **Be sure to remind the participant to try and refrain from smoking the night before the appointment and not to use a patch or lozenges on the morning of the appointment. Also, remind them to bring all used and unused patches, patch packets, and lozenge quit tubes back to the next appointment.**
26. Upload the session recording to Box.com (MOP, pg. 14) and complete the Audio Recording Length form in REDCap.

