## **Week 5**

1. Check to see if any information on participant's contact sheet needs to be updated.
2. Administer the CO test. Refer to the CO directions under the "CO Monitor" section on **Page 8** of this manual. Record the CO level in REDCap.
  - If the CO level is 3 or below, you need to administer a urine cotinine test to confirm that the participant is using nicotine products.
3. Collect the participant's Tobacco Use and NRT Use calendars and enter the data for the previous week into the appropriate SPSS database, then return the calendars to the participant.
4. Collect the used nicotine patches and lozenge quit tubes and dispose of them after reviewing the calendars. Any unused patches/lozenges can be given back to the participant.
5. Gather either the 21 mg patch or the 14 mg patch and give it to the participant. **(Patch dosage is based on number of cigarettes smoked determined at Baseline appointment). Be sure to write down the time that the patch is placed on their arm. Ideally, the participant should have the patch on for 30 minutes before the intervention begins.**
6. Have the participant fill out all of the questionnaires related to the session in REDCap, **except the Alliance Questionnaire, SECOND Minnesota Nicotine Withdrawal Scale and the SECOND Questionnaire of Smoking Urges.**
7. While the participant is filling out the questionnaires on REDCap, have REDCap open on the desktop and double check for participant entry errors as they progress through the questionnaires.
8. Tell the client that you are about to start the recording for the session. Explain that "this is a manualized intervention; therefore it will not feel like traditional therapy. We will be working from a manual and will adhere to the manual content, exclusively."

9. Turn on the recording and state your name, the date, and the time that you are starting the therapy. Do your best not to say the participant's name while being recorded.
10. Tell the participant to follow along in their client Intervention workbook as you go through your Therapist Intervention Manual. Let them know that the counseling could take up to 30 minutes and they are urged to write down information in their workbooks.
11. When appropriate, pause the audio recording and have the participant fill out the following:
  - **The Alliance Questionnaire**
  - **The second Minnesota Nicotine Withdrawal Scale**
  - **The second Questionnaire of Smoking Urges**

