    - Based on the participant's response to the Minnesota Nicotine Withdrawal Scale and the Questionnaire of Smoking Urges, graph the before and after scores in their workbook.
12. Un-pause the audio recording and continue the intervention by going over the participant's before and after scores for the Minnesota Nicotine Withdrawal Scale and Questionnaire of Smoking Urges.
13. Review each week and the participant's experience with the short-acting forms of NRT from the participant's manual. Answer any questions the participant has regarding the medications. Present the medication selection sheet, review it with the participant, and explain that they will be selecting their preferred short-acting NRT to use in conjunction with the patch for the rest of the medication period of the study. Once the participant has made a selection, enter it into REDCap and ask them to write it in their manual.
14. After the therapy, ask the participant if they have any questions. If they do not, tell them you are ending the recording.
15. Schedule the next appointment for the next week (preferably the same day of the week and the same morning time). This appointment should be scheduled with another study staff member other than the therapist who saw the participant for the five weekly sessions. Once you have it scheduled, make sure the appointment is placed in the [name] Lab Google Calendar.
16. Give the participant 6 patches. The 6 patches and the patch they are currently wearing (total of 7) will last through to the next appointment.
17. Give the participant enough of the short-acting NRT they chose to last through to the next appointment.
18. Have the participant sign for the medication in the medication sign-out log.
19. Mark in the Medication Inventory Excel sheet how many of the patches and gum packages/lozenge quit tubes/inhaler cartridges/nasal spray bottles you have given out so that we maintain a running total of prescriptions we have on hand.
20. Remind the participant of the instructions on how to use the patches and gum/lozenges/inhaler/nasal spray and let them know they can reference their workbook if they forget.
21. Give the participant a study phone and charger and instruct them to complete the EMA's daily.
22. Compensate the participant on their Greenphire ClinCard.

23. Give the participant an appointment card. Also, remind them to bring all used and unused patches, patch packets, and short-acting NRT back to the next appointment.

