11. Un-pause the audio recording and continue the intervention by going over the participant's before and after scores for the Minnesota Nicotine Withdrawal Scale and Questionnaire of Smoking Urges.
12. Review each of the short-acting forms of NRT with the participant. Answer any questions the participant has regarding the medications. Present the medication selection sheet, review it with the participant, and explain that they will be selecting their preferred short-acting NRT to use in conjunction with the patch for the rest of the medication period of the study. Once the participant has made a selection, enter it into REDCap and ask them to write it in their manual.
13. After the therapy, ask the participant if they have any questions. If they do not, tell them you are ending the recording.
14. Schedule the next appointment for the next week (preferably the same day of the week and the same morning time). This appointment should be scheduled with another study staff member other than the therapist who saw the participant for the five weekly sessions. **Once you have it scheduled, make sure the appointment is placed in the [name] Lab Google Calendar.**
15. Give the participant 7 patches. The patches will last through to the next appointment.
16. Give the participant enough of the short-acting NRT they chose to last through to the next appointment.
17. Have the participant sign for the medication in the medication sign-out log.
18. Mark in the Medication Inventory Excel sheet how many of the patches and gum packages/lozenge quit tubes/inhaler cartridges/nasal spray bottles you have given out so that we maintain a running total of prescriptions we have on hand.
19. Remind the participant of the instructions on how to use the patches and gum/lozenges/inhaler/nasal spray and let them know they can reference their workbook if they forget.
20. Make sure to give the participant the slip card.
21. Give the participant a study phone and charger and instruct them to complete the EMA's daily.
22. Compensate the participant on their Greenphire ClinCard.
23. Give the participant an appointment card. **Also, remind them to bring all used and unused patches, patch packets, and short-acting NRT back to the next appointment.**
24. Upload the session recording to Box.com (MOP, pg. 14) and complete the Audio Recording Length form in REDCap.

## Weeks 6, 9 & 13

### Week 6

1. Check to see if any information on participant's contact sheet needs to be updated.

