Standard of Care Group. Participants in the SC group will receive behavioral smoking cessation counseling based on best practice guidelines²⁶. This same four session counseling intervention was used in our previous smoking cessation intervention with participants in the criminal justice system and was found to be acceptable and feasible with low income populations. While this intervention does not focus exclusively on use of NRT, proper NRT use is covered as part of any standard behavioral intervention for smoking cessation²⁶. However, NRT will not be used in vivo during control sessions. Participants will be given a description of all four short-acting NRTs and will select one during their product selection session to use with the patch for smoking cessation throughout the intervention along with standard instructions for use. All counseling sessions will be approximately 30 minutes to match for therapeutic contact in the intervention group and will be conducted by RAs trained in the intervention and following the treatment manual (see draft client workbook in Appendix B).

Session 1: This session focuses on the harms of smoking and benefits of quitting. It will also cover behavioral factors associated with smoking including smoking as a habit, smoking cues, cognitive strategies to avoid smoking (e.g., distraction) and the physical symptoms related to nicotine withdrawal. Participants will learn coping strategies to deal with withdrawal and craving.

Session 2: Session 2 will focus on problem solving strategies to use for successful abstinence. The counselor will review common pitfalls associated with quitting such as refusing cigarettes from friends, weight gain, and sleep problems. Participants will be taught behavioral and cognitive strategies to combat these pitfalls. In addition, participants will be taught a brief relaxed breathing exercise to use during times of craving or when they have difficulties with sleep.

Session 3: This session of counseling will focus on behavioral changes made during the intervention (e.g., reducing number of cpd) and will discuss the importance of complete abstinence as the goal. Participants will be provided with strategies to reward themselves for abstinence including taking the money saved from buying cigarettes and using it for short-term and long-term rewards. In addition to reinforcements for abstinence, the counselor will review lapse behaviors and will stress the importance of abstinence as the goal.

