To test Aim 3, we will examine medication adherence during the 8 week intervention period between the intervention groups using Chi Square analyses at weeks 6, 9 and 13. Medication adherence will be defined as a self-reported use of taking 80% of medication as prescribed at each time point for both groups (adherent or not adherent). We can also look at adherence as a continuous proportion variable: adherence = number of doses taken / the number of doses given. We will also examine demographic and smoking characteristics (particularly withdrawal, cravings, abstinence self-efficacy, and NRT perceptions) that would be associated with medication adherence at weeks 6, 9 and 13 using logistic regression. These analyses will allow us to examine important associations with medication adherence in these groups.

To examine underlying factors believed to be important for medication adherence, particularly withdrawal, craving, self-efficacy, and perceptions of NRT, we will also examine these factors by intervention groups across time using paired t-tests, as appropriate. We are primarily interested in determining if our In vivo group had decreases in withdrawal and cravings, while increasing abstinence self-efficacy and NRT perceptions relative to the SC group. Given the pilot nature of this intervention, we will be able to examine 24-hour quit attempts and abstinence, but these factors are not the main focus on analyses as we will likely be underpowered to find significant differences on these outcomes with this small of a sample. While 80 participants may seem like a fairly large sample for a pilot study, a sample size between 500-600 participants is typical for most smoking cessation interventions and would be needed to examine important moderators and mediators of cessation. However, we will be able to obtain initial effect sizes that will be useful for determining the appropriate sample size for a fully-scaled R01 project in the future, if this intervention appears promising.

Missing data. There is a high likelihood that we will have participants who may miss an appointment, do not complete the study, or are otherwise lost to follow-up. Because of the potential of bias due to non-missing

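### At Week 5 the In vivo groups' first patch is placed in clinic and counted among the week's 7, while controls take all 7 home, so a patch-based Week 6 adherence score leans toward In vivo by about 0 to 9 points

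*Protocol*

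**What the plan says.** **Intervention Groups A to D.** Step 5 of the protocol's Week 5 list reads "Gather either the 21 mg patch or the 14 mg patch and give it to the participant", and staff are told: "Be sure to write down the time that the patch is placed on their arm". Step 16 hands over 6 more and counts the worn one: "The 6 patches and the patch they are currently wearing (total of 7) will last through to the next appointment". The Week 4 list for Group A tells the participant "not to use a patch or lozenges on the morning of the appointment", and the other groups get the same instruction for their own product. Under the protocol, then, the clinic patch is the Week 5 visit day's dose.

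**Control group.** Step 15 of the control Week 5 list reads "Give the participant 7 patches. The patches will last through to the next appointment". No step places a patch. The protocol's Brief Purpose of Study says "The Control group will not use NRT medication during the sessions", and the SAP's Standard of Care Group section agrees: "However, NRT will not be used in vivo during control sessions".

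**Outcome.** The SAP's Primary Outcomes section names medication adherence as the third primary outcome. At Weeks 6, 9 and 13, Aim 3 compares it between groups by chi-square, on this definition: "Medication adherence will be defined as a self-reported use of taking 80% of medication as prescribed at each time point for both groups". It also allows a continuous score, doses taken divided by doses given. Nothing in the SAP excludes a dose placed in clinic or sets a common counting window.

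**The concern.** The patch placed at Week 5 is part of the In vivo session. It is certain to be used, and it says nothing about what the participant does at home. Controls have no matching certain dose. With only 7 patches in the first interval, one guaranteed dose matters against an 80% cut.

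The test at Week 6 can therefore favour In vivo even when the two arms behave identically at home. Aim 3 is also meant to supply effect sizes for sizing a later full-scale trial, so an inflated Week 6 difference would carry forward.

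**Working it through.** **Inputs**

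- Week 5 patches: In vivo 6 + 1 worn = 7; control 7 + 0 = 7 (protocol, Week 5 lists). This reproduces the protocol's own total of 7.
- Window: Medication Dispensing gives 7 + 21 + 28 = 56 patches from Week 5 to Week 13. That is the 8-week treatment period, so the clinic patch lies inside it.
- Cut: the SAP words it both as 80% or more and as greater than 80%. Since 0.8 × 7 = 5.6, 5/7 = 71.4% and 6/7 = 85.7%, both wordings mean 6 of 7.
- Assumed, because the documents do not state them: the same probability p of using each take-home patch in both arms, 40 per arm, and two-sided 5%. The documents give no power calculation or alpha for adherence to reproduce.

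**Chance of being classed adherent at Week 6, patch only, no true effect**

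- In vivo (first patch certain): P(Bin(6, p) ≥ 5) = 6p⁵(1−p) + p⁶
- Control: P(Bin(7, p) ≥ 6) = 7p⁶(1−p) + p⁷
- Difference: 6p⁵(1−p)². This is the chance that the first patch would have been missed and exactly 5 of the other 6 used. It is positive for every p strictly between 0 and 1.

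For p = 0.8: In vivo 0.3932 + 0.2621 = 0.655; control 0.3670 + 0.2097 = 0.577.

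| p | In vivo | Control | Difference (points) | False-positive rate, 40 per arm |
|---|---|---|---|---|
| 0.7 | 42.0% | 32.9% | 9.1 | 13% |
| 0.8 | 65.5% | 57.7% | 7.9 | 11% |
| 0.9 | 88.6% | 85.0% | 3.5 | 8% |

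The maximum is 9.1 points, at p = 5/7. False-positive rates are exact enumerations of the uncorrected chi-square. With 28 per arm (70% of 40) they are 11%, 9% and 7%.

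**Continuous score.** The tilt is (1 + 6p)/7 − p = (1−p)/7: 4.3 points at p = 0.7 and 2.9 at p = 0.8.

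**If use clusters within people** (beta-binomial, mean use 0.7 to 0.9, 40 per arm)

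| ICC | Difference (points) | False-positive rate |
|---|---|---|
| 0.2 | 2.6 to 5.3 | 6 to 8% |
| 0.5 | 1.2 to 2.6 | 5 to 6% |
| 0.8 | 0.4 to 0.9 | 5 to 6% |

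**If patch and short-acting doses are pooled.** Take 7 patches plus 70 lozenges (10 a day for 7 days) = 77 doses, with a cut of 62. The tilt is 0.4 points at p = 0.7 and 2.3 at p = 0.8.

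**Weeks 9 and 13.** Both arms take all 21 and all 28 patches home, so scores by interval are unaffected. Scored cumulatively from Week 5 (28 and 56 patches, cuts 23 and 45), the tilt is at most about 4 and 3 points.

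**Check of the fix.** On the same 6 post-visit days both arms need 5 of 6, so at p = 0.8 the result is 65.5% in each. Dropping the clinic patch from In vivo alone does not repair the 80% endpoint: 5 of 6 against 6 of 7 remains, still 65.5% against 57.7%.

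**The case against.** The strongest reply is that the effect is small and conditional. Independent daily use makes it largest, and adherence usually clusters within people. The SAP does not say whether adherence is scored on the patch, the short-acting product or both. This is a pilot in which feasibility and acceptability come first, and Week 6 is one of three time points. All of this stands. It limits the size and leaves the direction unchanged.

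A reader might infer something much larger: a control who first applies a patch the next morning has only 6 patch days and needs 6 of 6, which would widen the gap to 30 to 39 points. The documents do not support this. It requires every control to defer the first patch, a Week 6 visit exactly 7 days later, and a patch applied that morning not to count. The Week 5 lists do not ask participants to omit the patch on the Week 6 morning, so a next-morning starter can still have seven patch days.

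A reader might also take Weeks 9 and 13 to be safe. That holds only if they are scored by interval, which the SAP does not state.

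Finally, the premise rests on the protocol's Week 5 procedure. The SAP describes staff placing a patch only in Sessions 1 to 4, on participants told to arrive wearing one, and its Product Selection section mentions no placement at Week 5. The two documents disagree, but the protocol steps are explicit and identical in all four groups.

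**Conclusion.** The concern holds in a limited form. If Week 6 adherence is scored on patches as doses taken over doses given with the 80% cut, and the protocol's Week 5 steps are followed, In vivo participants who attend that visit need 5 of 6 unsupervised patches and controls need 6 of 7. Equal home behaviour then gives a spurious In vivo advantage of about 0 to 9 points. The upper part of that range, 4 to 9 points with a Week 6 false-positive rate of about 8 to 13%, needs independent daily use at p = 0.7 to 0.9, 40 per arm and two-sided 5%. Clustering within people or pooling with short-acting doses brings it down to a few points or less. The direction needs none of these size assumptions. It is worth correcting because adherence is a primary outcome and the correction is cheap.

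**What to change.** In SAP Aim 3:

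- Exclude the Week 5 visit day from numerator and denominator in both arms.
- Score Week 6 patch adherence from the day-level Time Line Follow-Back over days 1 to 6 after the Week 5 visit in both arms, ending earlier if the Week 6 visit is earlier. The cap is needed because the protocol lets visits slip by a week or more, and In vivo leaves with 6 newly dispensed patches against control's 7. Capped, the window never exceeds the 6 patches both arms hold.
- Use returned patches only as a check. They carry no dates, and In vivo participants may be given back unused sampling-week patches.
- If Weeks 9 and 13 are scored cumulatively, start them from the same day 1.
- State whether adherence is scored for the patch, the short-acting product or both.

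The cost is a few sentences in the SAP and a Week 6 window one day shorter. No new data or dispensing change is needed.

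Separately, the SAP (Session 1, Sessions 2-4, Product Selection) and the protocol (Week 4 and Week 5 lists) disagree on whether In vivo participants arrive wearing a patch and whether one is placed at Week 5. These passages must be reconciled.

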## Intervention Group B

### Week 1

1. Check to see if any information on participant's contact sheet needs to be updated.
2. Administer the CO test. Refer to the CO directions under the "CO Monitor" section on Page 8 of this manual. Record the CO level in REDCap.
  - If the CO level is 3 or below, you need to administer a urine cotinine test to confirm that the participant is using nicotine products.
3. Gather either the 21 mg patch or the 14 mg patch and give it to the participant. (Patch dosage is based on number of cigarettes smoked determined at Baseline appointment). Be sure to write down the time that the patch is placed on their arm. Ideally, the participant should have the patch on for 30 minutes before the intervention begins.
4. Gather the 4mg or 2mg nicotine lozenge and give it to the participant to use. (Lozenge dosage is based on how soon participant smokes their first cigarette after waking, as reported at Baseline appointment). Wait to give the lozenge to the participant until the session is being recorded.
5. Have the participant fill out all of the questionnaires related to the session in REDCap, except the Credibility Expectancies Questionnaire, SECOND Minnesota Nicotine Withdrawal Scale and the SECOND Questionnaire of Smoking Urges.
6. While the participant is filling out the questionnaires on REDCap, have REDCap open on the desktop and double check for participant entry errors as they progress through the questionnaires.
7. Tell the client that you are about to start the recording for the session. Explain that "this is a manualized intervention; therefore it will not feel like traditional therapy. We will be working from a manual and will adhere to the manual content, exclusively."
8. Turn on the recording and state your name, the date, and the time that you are starting the therapy. Do your best not to say the participant's name while being recorded.
9. Give the participant the assigned client Intervention workbook and tell them to follow along as you go through your Therapist Intervention Manual. Let them know that the counseling could take up to 30 minutes and they are urged to write down information in their workbooks.
10. When appropriate, pause the audio recording and have the participant fill out the following:
  - **The second Minnesota Nicotine Withdrawal Scale**
  - **The second Questionnaire of Smoking Urges**

- **Based on the participant's response to the Minnesota Nicotine Withdrawal Scale and the Questionnaire of Smoking Urges, graph the before and after scores in their workbook.**

11. Un-pause the audio recording and continue the intervention by going over the participant's before and after scores for the Minnesota Nicotine Withdrawal Scale and Questionnaire of Smoking Urges.
12. Go over the Tobacco Use and NRT Use calendars.
13. Provide them with the copies of the calendars (in their folder) to keep in their pocket/wallet for use when they do not have their manual with them.
14. After the therapy, ask the participant if they have any questions. If they do not, tell them you are ending the recording.
15. Schedule the next appointment for the following week (preferably the same day of the week and the same morning time). **Once you have it scheduled, make sure the appointment is placed in the [name] Lab Google Calendar.**
16. Instruct the participant to **bring the calendars and workbook back so they can be reviewed next session.**
17. Give the participant 6 patches. The 6 patches and the patch they are currently wearing (total of 7) will last through to the next appointment.
18. Give the participant one box of lozenges (3 quit tubes = 72 lozenges). The 72 lozenges should last through to the next appointment if the participant uses 10 daily as advised. **Be sure to emphasize they are not to use the lozenges on the morning of the next appointment.**
19. Have the participant sign for the medication in the medication sign-out log.
20. Mark in the Medication Inventory binder how many of the patches and quit tubes you have given out so that we maintain a running total of prescriptions we have on hand.
21. Remind the participant of the instructions on how to use the patches and lozenges and let them know they can reference their workbook if they forget. Give the participant the instructions sheet.
22. Compensate the participant on their Greenphire ClinCard.
23. Give the participant an appointment card. **Be sure to remind the participant to try and refrain from smoking the night before the appointment and not to use a patch or lozenges on the morning of the appointment. Also, remind them to bring all used and unused patches, patch packets, and lozenge quit tubes back to the next appointment.**
24. Upload the session recording to Box.com (MOP, pg. 14) and complete the Audio Recording Length form in REDCap.

